4. SELECTION AND ENROLLMENT OF PARTICIPANTS

4.1 Inclusion Criteria

Participants must meet all of the relevant inclusion criteria to participate in the study.

Phase 1 (Focus Group) Inclusion Criteria – Adolescents

These are designed to be similar to inclusion criteria for Phase 2 and 3, but because adolescents will not be participating in the yoga intervention and are only attending a single focus group, criteria is more inclusive than Phase 2 and 3 to reduce assessment burden.

- a) Adolescents must have elevated depressive symptoms, defined by a score of 8 or higher on the PHQ-8, and a "1" or greater on at least one of the following two items: sad mood, or

anhedonia.

- b) Adolescents must be aged 13-18.
- c) Adolescents must be medically cleared for moderate physical activity by their primary care physician. This criterion will be assessed by adolescent or parents self-report that the adolescent has a current (dated in the past year) statement from their pediatrician that the adolescent may participate in school or camp programs including physical education.
- d) Adolescents must be able to read and write English sufficient to complete informed consent and engage in interventions.
- e) Adolescents aged 13-17 must assent to be in the study, and their parent/legal guardian must consent to their participation. Adolescents aged 18 must consent to be in the study.
- f) Able to attend a focus group.

Phase 2, Phase 3 Study A, and Phase 3 Study B Inclusion Criteria – Adolescents

Please note, inclusion criteria for Phase 2, Phase 3 Study A, and Phase 3 Study B are identical, with the exception that, for Phase 3/Study B, we will not require elevated depressive symptoms (a) or stable treatment (b).

- a) Adolescents must have elevated depressive symptoms, defined by a score of 10 or higher on the Quick Inventory of Depression –Adolescent Version-- Clinician Rating (QIDS-A-CR; [12-14]), including endorsement of either sad mood or anhedonia on the QIDS.
- b) Other treatment for depression must be stable at baseline. Adolescents do not have to be in other treatment for depression, but, if they are, it must be stable with no substantive changes for the past 8 weeks. If unexpected changes in treatment occur during the study protocol period, participants can remain in the study and this treatment change will be captured as data.
- c) Adolescents must be aged 13-18.

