4.2 Exclusion Criteria

Phase 1 (Focus Group) Exclusion Criteria – Adolescents

- a) Adolescents may not have current suicide ideation or behavior that warrants immediate treatment. They may have passive ideation (i.e., thoughts that life is not worth living), but

may not have active suicide ideation, intent, plan, or an attempt within the previous 6 months. We will not actively assess this for Phase 1, but we will exclude an adolescent if they indicate they have active suicide ideation.

- b) Adolescents cannot currently be engaged in yoga classes, as these are the study interventions.

Phase 2, Phase 3 Study A, and Phase 3 Study B Exclusion Criteria – Adolescents

Exclusion criteria for Phase 2, Phase 3 Study A, and Phase 3 Study B are identical.

- a) QIDS- A-SR may not be higher than a score of 21. This ensures that adolescents are not severely depressed.
- b) Adolescents may not meet criteria for the following:
 - i. Autism spectrum disorder (AS) “cannot be ruled out” (via MINI), and symptoms are of sufficient severity to interfere with study treatment per clinician judgment;
 - ii. Current psychotic disorder
 - iii. Lifetime history of a manic episode
 - iv. Anorexia or Bulimia in past 3 months
 - v. Substance use disorders in past 12 months, and symptoms are of sufficient severity to interfere with study treatment per clinician judgment

These will be assessed with the Mini-International Neuropsychiatric Interview (MINI).

- c) Adolescents may not have current untreated active suicide ideation or behavior. They may not have had a suicide attempt in the previous 6 months. They may not have suicide ideation that is so severe that the study clinician judges it will interfere with study participation (e.g., if the clinician judges they need a higher level of treatment now or potentially very soon). This means that adolescents with active suicide ideation may be included if they are receiving stable mental health services (e.g., therapy, counseling) and suicidal ideation is known to the mental health provider. Adolescents may be included if they have passive ideation (i.e., thoughts that life is not worth living) but are not in active treatment.
- d) Adolescents cannot currently be engaged in yoga classes, as this is the study intervention.
- e) Adolescents cannot be pregnant as yoga should be modified for pregnancy [15].

Parent Exclusion Criteria for all Phases

None. Please see parent inclusion criteria above.

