Given that all participants will have risk factors for suicidality (i.e., depression), some participants may experience suicide ideation or behavior in the course of study participation. Significant risk for suicide will be defined by QIDS item 12 score of 1 or greater (indicating suicide ideation or intent or behavior) OR the report of a desire or intent to hurt oneself to study staff. Whenever staff members identify an individual with significant risk for suicidality, we will use a standard protocol for managing this problem. Study staff will contact either [name], [name], or [name]. They will be available during regular business hours, and have extensive experience managing this issue. After hours, there is always a licensed mental health clinician available on call by cell phone.

When a clinician is asked to conduct an immediate evaluation, they will conduct a suicide risk assessment. The clinician will determine whether it is necessary to take immediate action to prevent the participant from causing harm to themselves. If needed, the study clinician may ask to speak to a parent and/or have a family member or ambulance bring the person to Butler Hospital or another hospital. If the participant is not in immediate danger of hurting themselves, we will take the following actions. First, we will work to develop a safety plan with the patient and encourage them to discuss this with their parents and/or treatment providers. Second, we will inform the parent(s) (for participants aged 13-17) to ensure that they are aware of the seriousness of the participant's symptoms and their suicidal ideation. If participants are 18, we will ask for permission to talk with a family member. Families will receive detailed psychoeducation regarding suicide risk including removing potential suicide means (e.g., guns, knives); being alert to mood changes, suicidal statements, etc.; and learning how to obtain emergency services. Finally, we will contact their primary care physician or other clinician to inform them of the suicidality. We will urge the participant/parent to make an appointment with that provider to discuss treatment options. Regardless of outcome, suicide assessments are always documented in writing.

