Participants may also show significant clinical deterioration, as defined as a QIDS total score of 16 or greater and an increase in QIDS score of 6 or greater from the previous QIDS assessment. This will also trigger a clinical evaluation and a determination of the best course of action for the adolescent based on clinical judgment. Typically, this will include notification of a parent and outpatient mental health provider (if the participant has one) or offer of referrals to an outpatient provider. Actions could also include facilitation of higher levels of care (e.g., inpatient hospitalization).

A participant who has undergone a suicide risk assessment or who has had clinical deterioration may continue to participate in the study unless the study PIs, in concert with the participant's parent and healthcare providers, deem study participation to increase risk for this particular participant. Participants who are hospitalized due to concerns about suicidality may be discontinued from the study if parents/

clinicians/ MPIs determine it to be in the best interest of the participant. However, they may also continue if that is determined to be in the best interest of the participant.

Additional Protections for Vulnerable Subjects

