7.1 Specification of Safety Parameters

Safety issues will be minimal in Phase 1 given that participation involves only a single focus group, no yoga classes, and no formal assessment of suicidality. However, should an issue arise (e.g., a voluntary report of suicide ideation from one of the adolescent participants), staff would manage it in the same way that they would manage it in Phases 2 and 3.

Please see Table 3 for a summary of safety issues, how they are assessed, when they are assessed, and relevant staff actions.

Table 3. Assessment and Management of Safety Issues, Summary, Phases 2 and 3.

| Safety Issue | How assessed | When Assessed in Phase 2/Phase 3 | Relevant Research Staff Actions |
|------------------------|--|---|---|
| Suicidality | QIDS, BDI, MINI Participant/parent report to research staff | B1, M1, M2, M3, M6*, M9* B1, M3, M6*, M9* Any point | Immediate clinical assessment as described in DSMP |
| Clinical deterioration | Change in QIDS score | M1, M2, M3, M6*, M9* | Immediate clinical assessment as described in DSMP |
| Injuries due to yoga | Structured self-report | Weekly during first 3 months | Follow until resolution; may result in changes to yoga instructor manual |
| Pregnancy | Single interview question | BL1 (exclusion) M1, M2 | Discontinuation from intervention |
| Other AEs | SAFTEE CASA Participant/parent report to research staff | M3 BL1, M3, M6*, M9* Any point | If related to study participation, follow resolution; potential changes to procedures particularly if AE is also unexpected |

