7.3 Adverse Events and Serious Adverse Events

Adverse Event (AE) definition: An adverse event (AE) is any unfavorable and unintended diagnosis, symptom, sign (including an abnormal laboratory finding), syndrome or disease which either occurs during the study, having been absent at baseline, or if present at baseline, appears to worsen. Adverse events are to be recorded regardless of their relationship to the study intervention.

Serious Adverse Event (SAE) definition: A serious adverse event (SAE) is one that meets one or more of the following criteria:

- Results in death
- Is life-threatening (places the subject at immediate risk of death from the event as it occurred; includes a suicide attempt or drug overdose)
- Results in inpatient hospitalization or prolongation of existing hospitalization
- Results in a persistent or significant disability or incapacity
- Results in a congenital anomaly or birth defect

An important medical event that may not result in death, be life threatening, or require hospitalization may be considered an SAE when, based upon appropriate medical judgment, the event

may jeopardize the subject and may require medical or surgical intervention to prevent one of the outcomes listed in this definition.

Study staff will record all reportable events with start dates occurring any time after informed consent is obtained at least until the final day of study participation. Each time participants attend yoga classes, we will inquire about injuries due to yoga. For all participants in either the open trial or pilot RCT, at Month 3 (end of intervention), study staff will administer the SAFTEE in order to inquire about the occurrence of AE/SAEs during the previous 3 months. This allows us to systematically assess number of adverse events, severity, and resulting impairment. Finally, any time a participant (or parent) reports an adverse event to any staff member, a research assistant will contact the participant or parent or both to ascertain information for recording of the adverse event. For adverse events ascertained by any of these three possible methods, the research assistant gets information on what happened, start and stop dates, severity, functional impact, interactions with healthcare professionals, perceived cause, and possible relation to study participation.

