7.4 Reporting Procedures

Once staff members report an AE or SAE to MPIs, [name] or [name] (and only [name] in Phase 3, as she is not blind in Phase 3) will code severity, causal relationship, and whether the event was expected. If necessary, she will seek further information from the participant or parent or other source before coding.

AEs will be coded on a weekly basis. Any potential SAE will be immediately reviewed by one of the MPIs (or a qualified designee in her absence) and coded; this coding will subsequently be reviewed by the SMC (Safety Monitoring Committee). Coding of AEs and SAEs occurs on a study AE case report form.

SAEs that are unanticipated, serious, and possibly related to the study intervention will be reported to the Safety Monitoring Committee (SMC), IRB, and NCCIH in accordance with requirements. We will use the Butler Hospital IRB-approved AE report form.

- Unexpected fatal or life-threatening SAEs related to the intervention will be reported to the IRB, NCCIH Program Officer, and SMC within 3 days of the investigator becoming aware of the event. Other serious and unexpected SAEs related to the intervention will be reported within 7 days. These timeframes follow guidance from NCCIH and are consistent to local IRB policies.

Anticipated or unrelated SAEs will be handled in a less urgent manner but will be reported to the SMC, IRB, and other oversight organizations in accordance with their requirements, and will be reported to NCCIH on an annual basis.

- Unrelated SAEs that are fatal or life threatening must be reported to the Butler Hospital IRB within 7 days of the investigator becoming aware of the event.
- Unrelated SAEs that are not fatal or life-threatening must be reported to the Butler Hospital IRB annually.

All other AEs documented during the course of the trial will be reported to NCCIH on an annual basis by way of inclusion in the annual report and in the annual AE summary which will be provided to NCCIH and to the SMC. The SMC Report will state that all AEs have been reviewed.

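### The QIDS deterioration trigger compares only with the previous visit, so gradual worsening without suicidality can accumulate with no evaluation required; add baseline as a second reference

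*Combined protocol and SAP*

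**What the plan says.** Section 7 defines significant clinical deterioration by two conditions that must hold together: "defined as a QIDS total score of 16 or greater and an increase in QIDS score of 6 or greater from the previous QIDS assessment". Meeting it triggers a clinical evaluation, which typically leads to notifying a parent and any outpatient provider, or to referral.

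The Schedule of Evaluations (Section 6.1, Table 2) places the clinician-rated adolescent QIDS at baseline and Months 1, 2, 3, 6 and 9, with adolescent and parent both assessed. Month 9 applies only to those who signed an earlier consent form. Table 3 (Section 7.1) describes the deterioration check only as "Change in QIDS score" and refers to the DSMP for the response.

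Phase 2 and Study A require "a score of 10 or higher on the Quick Inventory of Depression" at entry (Section 4.1); Study B waives that minimum. Section 4.2 sets an upper limit on the self-report form, which "may not be higher than a score of 21. This ensures that adolescents are not severely depressed".

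Suicidality has its own trigger: "Significant risk for suicide will be defined by QIDS item 12 score of 1 or greater", or a report to staff of wanting or intending to hurt oneself. Section 9.1.2 gives the QIDS a safety role for both deterioration and suicidality, but adds no second numerical definition of deterioration.

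**The concern.** Because the comparison is always with the last visit, a rise of up to 5 points is tolerated at each assessment and then becomes the new reference. The rule detects jumps well. It can miss a slow decline that in total exceeds its own 6-point threshold several times over.

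The other routes in the available text do not require an evaluation on depression severity:

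- The Section 7 suicide-risk rule and the BDI and MINI suicide items act on suicidality, not on total score.
- Section 7.3 counts as an adverse event something "having been absent at baseline, or if present at baseline, appears to worsen", and Section 7.4 says "AEs will be coded on a weekly basis". Coding is not a clinical evaluation, and Section 9.1.2 says deterioration is not necessarily an adverse event.
- Section 8 allows an investigator to contact a provider or parent about worsening depression, but leaves this to discretion.

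At stake is the safety of depressed 13 to 18 year olds who worsen steadily without disclosing suicidality. No planned analysis, sample size or stated commitment is affected.

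**Working it through.** **Inputs from the protocol.** Trigger: total ≥ 16 and rise ≥ 6 from the previous QIDS (Section 7). Visits: baseline, M1, M2, M3, M6, M9 (Table 2). Study A baseline 10 to 21 (Sections 4.1 and 4.2; the upper limit names the self-report form and is applied here to the clinician-rated score). Study B has no minimum.

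**Assumptions.** The protocol does not give the QIDS range. I take a maximum of 27, or 24 when item 12 is zero.

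**Rules compared.** At visit *i* with score *S*:

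- Current: *S_i* ≥ 16 and *S_i* − *S_(i−1)* ≥ 6.
- Proposed: *S_i* ≥ 16 and (*S_i* − *S_(i−1)* ≥ 6 or *S_i* − *S_BL* ≥ 6).

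**Observed paths.**

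| Path from baseline | Current rule | Proposed rule |
|---|---|---|
| 10-16 | fires at M1 (+6) | fires at M1 |
| 10-14-18-22 | silent (+4, +4, +4; total +12) | fires at M2 (18 − 10 = 8) and M3 (22 − 10 = 12) |
| 9-15-20 (Study B) | silent (the +6 ends at 15, below 16; then +5) | fires at M2 (20 − 9 = 11) |
| 14-8-16 | fires at M2 (+8) | fires at M2; a baseline-only rule would not (+2) |
| 18-12-16-20 | silent (+4, +4 after the low) | silent (20 − 18 = 2) |

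**Largest silent rise by M3, Study A baseline.** All integer paths were enumerated. With item 12 zero (cap 24), the maximum is 14 (10-15-20-24). With a cap of 27 that ignores item 12, it is 15 (10-15-20-25). Under the proposed rule the maximum from a baseline of 10 is 5.

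**Detection of a true decline with measurement error.** True path 10-14-18-22, normal visit error, scores rounded and clipped to 0-27, observed baseline 10 to 21, all visits attended. Share firing at least once by M3:

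| Error SD | Current | Proposed |
|---|---|---|
| 1.0 | 33% | about 100% |
| 1.5 | 53% | about 100% |
| 2.0 | 64% | 99% |
| 2.5 | 71% | 97% |
| 3.0 | 75% | 95% |

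**Cost in participants with no true change.** True baseline mean 14 and SD 3, same error model, repeat triggers counted. Extra evaluations per 34 Study A participants, proposed minus current:

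| Error SD | Through M3 | Through M6 | Through M9 (if all had it) |
|---|---|---|---|
| 1.0 | 0.0 | 0.0 | 0.0 |
| 1.5 | 0.2 | 0.3 | 0.4 |
| 2.0 | 1.0 | 1.5 | 2.0 |
| 2.5 | 2.0 | 3.0 | 4.0 |
| 3.0 | 2.9 | 4.4 | 5.8 |

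At SD 3, total evaluations through M3 go from 7.5 to 10.4, and the share ever flagged goes from about 21% to 26%. Adding 20 stable Study B participants with no minimum score gives at most 4.7, 7.1 and 9.5 extra through M3, M6 and M9.

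**The case against.** A previous-visit rule with a severity floor is a legitimate way to detect acute change. It sits beside the suicidality triggers, on-call clinicians, continuing outside treatment and discretionary contact. The response to deterioration is delegated to the DSMP, which may contain a further criterion. This stands: whether the gap exists in the operating safety plan cannot be settled from the protocol.

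Measurement error also helps the current rule. A reader might infer that a teen declining along 10-14-18-22 would always go unflagged. That holds only for that exact observed sequence; for a true decline of that shape the current rule already fires in a third to three quarters of cases. At error SD 3, where the added cost is highest, it catches about 75%.

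Table 2 schedules the QIDS for adolescent and parent, and Section 7 does not say which series the trigger uses. Where a parent takes part, which is optional, the parent's scores might fire when the adolescent's do not. The calculations model one series only.

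The change has costs beyond clinician time. Evaluations typically lead to parent and provider notification, a confidentiality cost for adolescents. Section 6.2.3 lets either principal investigator do risk assessments, so more triggers mean slightly more contact with the blinded one.

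These points limit the size of the gap but do not remove it: nothing else in the available text requires an evaluation on cumulative worsening.

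**Conclusion.** The point holds as a cheap improvement to safety monitoring. On the available text, the trigger has no cumulative reference. An adolescent can be observed to rise 12 points by Month 3, and at most 14 with item 12 at zero, without a required evaluation on QIDS severity. Adding baseline raises detection of a true 10-14-18-22 decline from about 33%-75% to about 95%-100%.

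The score caps, error SDs and baseline distribution are assumptions. The protocol gives no rate of gradual worsening, so how often this would occur is unknown.

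Three stronger readings are not supported. The 15-point figure should not be quoted for a teen with item 12 at zero, because it needs a total of 25 against an assumed 24 available. A final score of 22 does not breach the limit of 21, which is an entry criterion on the self-report form. The protocol does not break a commitment of its own, since it nowhere promises a baseline comparison.

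**What to change.** In Section 7, define significant clinical deterioration as a QIDS total of 16 or greater together with an increase of 6 or greater from the previous QIDS assessment or from baseline. Put the same definition in the Table 3 cell, and state whether it applies to the adolescent's series, the parent's, or both. Keep the previous-visit reference: replacing it would lose cases such as 14-8-16. If the DSMP already has a baseline criterion, copy that wording into the protocol instead.

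No new assessment is needed. Under the stated assumptions, the cost per 34 stable teens is about 0 to 3 extra evaluations through Month 3, 0 to about 4 through Month 6, and 0 to about 6 if all had Month 9, with the notifications that follow. These counts include repeats: a teen who stays at 16 or more and at least 6 above baseline fires at every later visit.

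The change does not catch relapse after improvement (18-12-16-20). Using the lowest prior score as a reference would cover that, but its added cost has not been worked out here.

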7.1 Specification of Safety Parameters

Safety issues will be minimal in Phase 1 given that participation involves only a single focus group, no yoga classes, and no formal assessment of suicidality. However, should an issue arise (e.g., a voluntary report of suicide ideation from one of the adolescent participants), staff would manage it in the same way that they would manage it in Phases 2 and 3.

Please see Table 3 for a summary of safety issues, how they are assessed, when they are assessed, and relevant staff actions.

Table 3. Assessment and Management of Safety Issues, Summary, Phases 2 and 3.

| Safety Issue | How assessed | When Assessed in Phase 2/Phase 3 | Relevant Research Staff Actions |
|------------------------|--|---|---|
| Suicidality | QIDS, BDI, MINI Participant/parent report to research staff | B1, M1, M2, M3, M6*, M9* B1, M3, M6*, M9* Any point | Immediate clinical assessment as described in DSMP |
| Clinical deterioration | Change in QIDS score | M1, M2, M3, M6*, M9* | Immediate clinical assessment as described in DSMP |
| Injuries due to yoga | Structured self-report | Weekly during first 3 months | Follow until resolution; may result in changes to yoga instructor manual |
| Pregnancy | Single interview question | BL1 (exclusion) M1, M2 | Discontinuation from intervention |
| Other AEs | SAFTEE CASA Participant/parent report to research staff | M3 BL1, M3, M6*, M9* Any point | If related to study participation, follow resolution; potential changes to procedures particularly if AE is also unexpected |

